5.0	Registration Procedures
6.0	Radiation Therapy
7.0	Drug Therapy
8.0	Other Therapy
9.0	Patient Assessments
10.0	Data Collection
11.0	Statistical Considerations
12.0	Data Safety Monitoring Plan
	References
	Appendix I - Sample Treatment Consent Form Appendix II - Study Parameters Appendix IV - Performance Status Scoring Appendix IV - Staging System Appendix V - Comorbidity Scoring Sheet and Charlson Comorbidity Index (CCI Appendix VI - Cost Effectiveness Analysis Worksheet Appendix VII - FACT-L Worksheet Appendix IX - EQ-5D Worksheet

Schema

Number of patients = 226 (113) per arm)

ELIGIBILITY (see section 3.0 for full criteria)

- Stage II-III or Recurrent (after surgical resection) non-small cell lung cancer (NSCLC) that would benefit from local radiation therapy.
- Zubrod performance status of 2 or greater
- OR Zubrod performance status 0-1 and weight loss > 10% over the last 6 months prior to enrollment OR medically unable to tolerate or refusing standard combined modality therapy
- -Total (aggregate) gross tumor volume ≤ 500 cm³ (500 cc's or 0.5 Liters
- No prior radiotherapy to the chest or neck that would result in overlap of radiation therapy fields
- No chemotherapy within one week prior to study registration/study enrollment except concurrent chemotherapy may be given at the investigator's discretion to patients randomized to the standard arm (arm B, 30-33 fractions)
- Study-specific consent form signed

Eligibility Checklist

not permitted. Subjects must meet all of the inclusion and exclusion criteria to be registered to ment may not begin until a subject is registered.
 (Y) 1. Does the patient have histologically or cytologically documented NSCLC within 9 months of study enrollment?
 (Y) 2. Is TNM Stage II or III or does the patient have recurrent disease after surgical resection?
 What is the patient's TNM stage?
 (N) 3. Has the patient had prior radiotherapy to the chest or neck that would result in overlap of radiation therapy fields?
 (Y) 4. Is the Zubrod performance status 2 or greater?
 What is the patient's performance status (see Appendix III)?
 (Y) If not, does the patient have weight loss > 10% over the last 6 months?
 (Y) If not, is the patient medically unable to tolerate or refusing standard combined modality therapy?
 (Y) 5. Is the total (aggregate) gross tumor volume \leq 500 cm 3 (500 cc's or 0.5 Liters)
 (Y) 6. Is patient ≥ 18 years of age?
 (N) 7. Has the patient had any chemotherapy within a week prior to study registration/study enrollment?
 (Y/Quit/Never) 8. Does the patient smoke?
 (Y) 9. Were all the required pre-registration/study enrollment evaluations administered as specified in Section 4, including CT with contrast of lung and upper abdomen within 12 weeks of registration/study enrollment?
 (Y/NA) 10. Has the patient agreed to use an effective method of contraception? Women of child-bearing potential and men must agree to use adequate contraception (hormonal or barrier method of birth control; abstinence) prior to study entry, for the duration of study participation, and for 90 days following completion of therapy. Should a woman become pregnant or suspect she is pregnant while participating in this study, she should inform her treating physician immediately.

10a. A female of child-bearing potential is any woman (regardless of sexual orientation, having undergone a tubal ligation, or remaining celibate by choice) who meets the

following criteria:

- * Has not undergone a hysterectomy or bilateral oophorectomy; or * Has not been naturally postmenopausal for at least 12 consecutive months (i.e., has had
- * Has not been naturally postmenopausal for at least 12 consecutive months (i.e., has had menses at any time in the preceding 12 consecutive months).

 (N) 11. If female, is the patient pregnant or lactating?
(Y) 12. Has the patient signed the protocol consent?

1.0 Introduction

1.1 Locally Advanced NSCLC and Radiation Therapy

Lung cancer is the leading cause of cancer-related mortality in the United States each year with an estimated 215,000 new cases and over 160,000 deaths, [1]. The majority of these, approximately 80%, are non-small cell lung cancers (NSCLC). Only 15-20% of these cases present with early or

localized disease and the rest are more advanced, with large tumors, regionally involved lymph nodes, or distant metastatic disease [2].

Surgical resection is the mainstay of treatment for stage I and II NSCLC, often followed by adjuvant chemotherapy. For stage III NSCLC, selected cases can be treated surgically, while for many patients, combined chemotherapy and radiation therapy is the best curative option. If a NSCLC patient has co-morbid conditions or poor performance status, the treatment options are more limited. Surgery may not be possible for curative treatment of early stage disease, and concurrent chemoradiation may not be tolerable as treatment of more advanced disease. Conventionally fractionated radiation therapy alone as definitive treatment for locally advanced NSCLC has poor survival rates, with a median survival of only 10 months in an RTOG trial that established 60 Gy as the standard dose[3]. Since then, there have been many efforts to increase the efficacy of radiation therapy for locally advanced lung cancer. Clinical trials have suggested a benefit from dose escalation. For example, A University of Michigan phase I study that included mainly stage III NSCLC, showed a 5 year overall survival improvement from 4% to 28% when dose was increased from 63-69 Gy to 92-103 Gy [4]. Also, a median survival of 24.7 months was achieved in 112 patients treated on four University of North Carolina phase I/II trials of high dose (60-90 Gy) radiation therapy in unresectable stage III NSCLC [5]. However, local failure remains a significant problem even with high dose radiation therapy, with local failure rates of 22-50% in multiple studies [5, 6].

The best method found to date for improving the efficacy of radiation therapy for locally advanced NSCLC is to combine it with chemotherapy. One of the early phase III trials showing a benefit to chemotherapy followed by radiation therapy was the CALGB 8433 trial, which showed a median survival increase from 9.6 to 13.7 months with the addition of chemotherapy [7]. Since then, multiple trials of locally advanced NSCLC in good performance status patients have shown even better outcomes with concurrent chemotherapy and radiation therapy, rather than sequential [8-12]. A recent randomized phase III trial even achieved a median survival time of 21.7 months in inoperable stage III NSCLC [13].

However, the better local control and survival achievable by adding chemotherapy to radiation therapy comes at the expense of increased toxicity. Some of the most commonly used chemotherapy combinations in locally advanced NSCLC are cisplatin/etoposide and carboplatin/paclitaxel. All of these agents are associated with myelosuppression, nausea, and vomiting and several are associated with neuropathy and nephrotoxicity. When given with radiation therapy, these toxic effects can be worsened and the adverse effects commonly seen with radiation therapy to the chest, such as esophagitis, can be intensified. The CALGB 8433 trial reported higher rates of serious adverse effects including neutropenic infections, vomiting, and severe weight loss in the group of patients receiving chemotherapy and radiation therapy [14]. Toxicity with concurrent chemoradiation therapy can be even greater than with sequential. RTOG 94-10 reported higher rates of acute grade 3-4 non-hematologic toxicity, including esophagitis, with concurrent compared to sequential chemoradiation therapy [9]. In a phase III trial by the CALGB and ECOG, patients receiving carboplatin with radiation therapy suffered more neutropenia, thrombopenia, and anemia than did patients receiving radiation therapy alone [15]. These adverse effects can decrease quality of life for patients and cause administration of combined modality therapy to be impractical in poor performance status patients.

Progress in technology has changed the delivery of radiation therapy to allow more precise targeting of tumor and avoidance of normal structures. 3D conformal radiotherapy (3-DCRT) and intensity modulated radiation therapy (IMRT), based on computed tomography (CT) planning are possible due to modern computer and software advances. These treatment techniques have allowed

reduction of treatment volumes and dose escalation of fractionated radiotherapy. RTOG 9311 showed the feasibility of delivering up to 83.8 Gy at 2.15 Gy per fraction for stage I-III NSCLC [6]. Recently, there has been increasing use of image-guided radiation therapy (IGRT), which involves frequent imaging to account for interfraction and sometimes intrafraction motion of the target and thus improves the accuracy of dose delivery. IGRT involves modalities such as daily ultrasound, kilvoltage (kV) imaging such as x-rays or kV cone beam CT, or megavoltage (MV) imaging such as helical MV CT or MV cone beam CT. Adaptive radiotherapy is the concept of using frequent imaging to alter treatment based on changes in the tumor or normal tissue during the course of treatment. This can be important in treatment of NSCLC since tumors can shrink considerably during treatment, allowing greater avoidance of normal structures when the treatment plan is modified. Kupelian et.al. reported an average decrease in the tumor volume of 1.2% per day in a study of 10 NSCLC patients [16]. Imaging can also be used to account for organ motion with respiration, which is crucial in treatment of lung tumors. One method to manage respiratory motion is by limiting tumor motion, using techniques such as abdominal compression or breath holding. The other method to account for respiratory motion is to allow free tumor motion but keep the target constantly in the beam's eye view when the beam is on, using techniques such as beam tracking, couch-based motion compensation, or respiratory gating.

All of these advances in treatment planning and delivery have allowed the development of stereotactic body radiation therapy (SBRT) as a promising treatment for early stage NSCLC. This treatment method combines the previously mentioned techniques with stereotactic targeting to allow a dramatic reduction in treatment volumes, enabling delivery of hypofractionated, ablative doses of radiation therapy. SBRT can be safely used in patients with co-morbid conditions or poor performance status and can achieve local control rates as high as 95% at 2 years [17]. The technological advances making possible SBRT in early stage NSCLC could be transferred to treatment of locally advanced NSCLC as well, to allow a shorter overall treatment time without increasing toxicity. Notably, the reported dose escalation trials for locally advanced NSCLC utilize 3-D conformal radiation therapy but do not include daily image guidance or methods for compensating for tumor motion with respiration. With these technological advances, it should be possible to further limit dose to normal tissue and thus treat lung tumors to a higher dose in fewer fractions of radiation therapy. This protocol will address the management of stage II-III NSCLC who are not candidates for surgical resection or stereotactic body radiation therapy as definitive treatment.

The study is designed to determine whether an accelerated course of hypofractionated radiation therapy with daily image guidance and motion assessment/control will allow more effective treatment of poor performance status patients with stage II-III NSCLC, who would benefit from local therapy compared to standard radiation therapy (60 Gy in 2 Gy per fraction). Poor performance status patients can be a heterogeneous group, with tumor-related factors, other co-morbidities, or advanced age placing patients in the category. These patients have traditionally been underrepresented in clinical trials, and thus no prospective study has evaluated the efficacy of other radiotherapy dose fractionations in these patients. One phase III trial of "poor-risk" locally advanced NSCLC (RTOG 93-04) included just over 40% Karnofsky performance status 60-70 patients and showed median survival times of 9.5 and 10.3 months with 60 Gy of conventional radiation therapy alone or with recombinant β-interferon [18]. 1 year overall survival was just 44% in these patients.

1.2 Rationale for Radiation Therapy Dose

A dose of 45 Gy in 15 fractions (3 Gy per fraction) has been commonly employed in the past to treat poor performance status NSCLC patients. A pilot study of accelerated radiation therapy with concurrent carboplatin/paclitaxel for stage III NSCLC was closed after enrollment of only 5 patients due to excessive toxicity. The radiation therapy dose used was 60 Gy in 4 weeks of daily treatment,

using a concomitant boost [19]. Our protocol is different in that it will not permit concurrent chemotherapy, it will not allow treatment of elective nodal regions as was done in that trial, and it will use daily image guidance so that treatment volumes will be significantly smaller. In a small study of 14 patients, Tsoutsou et.al. showed the feasibility of treating with 3.5 Gy daily for 15 fractions (52.5 Gy total) with a one week break after the 10th fraction, along with concurrent chemotherapy, in locally advanced non-small cell lung cancer PS 0-2 patients [20]. Slotman et.al. treated 301 stage III NSCLC patients with three different hypofractionated radiation therapy regimens of 40 Gy in 8-10 fractions with a one week break, 30-32 Gy in 6 fractions or 24 Gy in 3 fractions. These regimens were all well tolerated [21].

Standard radiation to the chest for unresectable stage III NSCLC is 60-66 Gy at 2 Gy per fraction. Radiobiologic calculations indicate that the accelerated therapy regimen of 3 Gy/fraction to 45 Gy is similar to 2 Gy per fraction to 60 Gy, with regrowth delay time (time to progression) of 92% and late complication biologically effective dose (BED) of 90% of that calculated for standard radiation. Additionally, 45 Gy at 3 Gy per fraction has been shown to have similar clinical outcomes and toxicity. This has been shown in a retrospective review at MD Anderson of 2 cohorts of node positive patients with inoperable LA-NSCLC treated with radiation alone [22]. One cohort (26 patients) had borderline prognostic factors (KPS < 70 but > 50 and/or weight loss of more than 5%) and was treated to 45 Gy over 3 weeks at 3 Gy/fraction. The second cohort (29 patients) had significantly better prognostic factors and was treated to 60-66 Gy over 6 to 6.5 weeks at 2 Gy per fraction during the same period. Despite having worse prognostic factors, the cohort treated to 45 Gy at 3 Gy per fraction over 3 weeks had response rates, locoregional control, and overall survival comparable to those in the cohort treated to a total dose of 60-66 Gy at 2 Gy per fraction over 6 weeks without difference in acute or late toxicity. Radiation dose intensification in locally advanced NSCLC has been studied in prospective trials. Slotman et.al. treated 301 stage III NSCLC patients with three different hypofractionated radiation therapy regimens of 40 Gy in 8-10 fractions with a one week break, 30-32 Gy in 6 fractions or 24 Gy in 3 fractions. These regimens were all well tolerated.[23] A group from Poland found similar toxicity profiles in patients treated with 21 fractions of radiation using 2.7, 2.8 and 2.9 Gy fractions. Of those patients, 7% had grade III acute esophageal toxicity and 6% had grade III or greater late pulmonary toxicity [24]. An Italian group reported a 30 patient trial wherein 60 Gy in 20 fractions was given to patients with locally advanced NSCLC. Grade 3 hematological toxicity occurred in 1 patient, grade 3 esophagitis in 1 patient and grade 3 pneumonitis in 2 patients [25]. Subsequently, the MD Anderson group reported a phase I trial evaluating 45, 52.5 and 60 Gy delivered in 15 fractions using proton beam and found similar, acceptable levels of toxicity in all arms[26]. Collectively, this information support both our trial concept and the dose intensity utilized.

Specifically, the experimental arm dose for this trial is based on a dose escalation trial at University of Texas Southwestern evaluating the maximum tolerated dose of hypofractionated IGRT in this patient population. Doses were escalated from 3 Gy per fraction (total dose 45 Gy) to 4.0 Gy per fraction (total dose 60 Gy) and evaluation for treatment related toxicity was being performed. Critical structure dose constraints will be expressed as organ dose-volume limits, with limits formulated with the approval of the study investigators using known tolerance data, radiobiological conversion models, and norms used in current practice at academic centers [27]. The trial design called for treating many patients per dose level, akin to a phase II trial, so as to collect outcome data on enough patients to simultaneously appreciate toxicity and efficacy in order to optimize dosing. The maximum tolerated dose (MTD) was never reached on this protocol up to 60 Gy in 15 fractions for effectively the same population treated on this protocol. 50 Gy, 55 Gy or 60 Gy in 15 fractions was delivered using image guided radiation therapy. Patents with tumor volumes larger than 500 cc were excluded. 18, 23 and 21 individuals were enrolled at each dose level respectively. The median follow-up is 195 days (range 26-927 days). Median follow-up is 452 days if patient deaths are censored in a population that succumbs commonly to non-cancer or treatment related causes. Of

the 52 patients enrolled, only 4 patients experienced grade 3 or higher treatment-related toxicity spread indiscriminantly among the tested dose levels. Long term tumor control from this trial is still being collected. Since previous trials described above show improving control and survival with radiation dose intensification and since the MTD was not reached, we have chosen the 60 arm to be the experimental arm of this protocol.

1.3 Comparative Economic Analysis

In the United States, total national health expenditures (NHE) increased from \$7.14 billion in 1990 to \$2.23 trillion in 2007, which represents an average annual growth rate of 7.0%. In contrast, over the same period, U.S. gross domestic product (GDP) increased from \$5.8 trillion in 1990 to \$13.8 billion, or average 5.2% annual growth rate. Given that national health expenditures have grown faster than GDP, the share of GDP devoted to health expenditures has increased from 12.3% in 1990 to 16.2% in 2007[28]. Moreover, national health expenditure growth is expected to continue to outpace income growth, with total NHE reaching \$4.35 trillion by 2018, accounting for 20.3% of GDP (CMS 2009). There is growing concern that these trends in health expenditures are not sustainable. For the Medicare program, current estimates of the present value of total unfunded liabilities through the year 2083 (the present value of the difference between projected future Medicare expenditures and Medicare revenues over the next 75 years under current Medicare policy) total \$89 trillion, with Medicare's Hospital Insurance ("Part A") trust fund projected to be depleted by 2017[29].

Prior studies have estimated that about half of the recent growth in health expenditures is attributable to advances in various forms of health technology, including new pharmaceutical products, surgical procedures, imaging modalities, and new biomarkers[29]. While almost all of these new technologies offer some potential to improve clinical outcomes, they also more often than not add to health expenditures. Within the context of unsustainable trends in health expenditures, a key policy question relates to whether the extent of improvement in outcomes associated with the use of a new technology is attained at a "reasonable" additional cost, compared to existing technology. Indeed, the value offered by new technologies is being subjected to increasing scrutiny by reimbursement authorities in many health systems worldwide. For example, in the United Kingdom, the National Health Service bases payment policy decisions for new technologies on recommendations from the National Institute for Health and Clinical Excellence (NICE), which in turn are substantially influenced by cost-effectiveness analysis yielding an estimated additional "cost per quality-adjusted life-year (QALY) gained" via use of the new technology. Currently, NICE usually considers technologies offering improved outcomes at a cost less than £20,000 to £30,000 per QALY gained (about \$33,000 - \$50,000) acceptable, though exceptions are common[30].

Therefore, we propose to collect cost information in both arms in this Phase III trial, and assess patients' health related quality of life, in order to evaluate the economical consequence of using the new technology proposed in this study and its impact on quality of life. We hypothesize that the new technology may be cost saving (cost less than the current standard of care) over the patient's entire treatment course, making it very attractive for adoption in treatment for lung cancer patients. Alternatively, we hypothesize that the new technology will increase quality-adjusted life-years for lung cancer patients (compared to the current standard of care) at a reasonable incremental cost, as defined by generally accepted cost-effectiveness thresholds.

1.4 Chemotherapy in Poor Performing Patients Enrolled On-study

Randomized trials that showed survival benefit for adding chemotherapy to radiotherapy generally excluded poor performing patients and often patients with significant weight loss. At trial initiation, our trial prohibited the use of specifically concurrent chemotherapy given with radiation based on the assumption that such therapy was not standard. Adjuvant chemotherapy, either prior to radiotherapy or afterwards, has been allowed since opening in either of the randomized arms.

However, with accrual, we have learned that medical oncologists use concurrent chemotherapy on a case by case basis such that the true population outcome is likely related to a more variable treatment with many getting radiotherapy alone, some getting adjuvant chemotherapy and some getting even concurrent chemotherapy. In a site guery, it was learned that the prohibition of allowing concurrent chemotherapy led both to lower accrual and some potential sites refusing to open the protocol. In response, we have amended the protocol to allow concurrent chemotherapy with radiotherapy using the popular and less toxic Carboplating/paclitaxel regimen in standard concurrent dosing specifically in the standard arm only (30 fractions). Our hypothesis testing regarding the higher potency of hypofractionated radiation in the experimental arm (15 fractions) would be disrupted if concurrent, radiosensitizing chemotherapy were given; hence, concurrent chemotherapy will not be allowed on the experimental arm in any circumstance. Survival estimates related to the power and sample size determination of the study in all likelihood will not be affected given that concurrent therapy has never been shown to be superior to radiation alone in poor performing patients. Nonetheless, we will perform a statistical sensitivity analysis at the time of the interim analysis (50% patient enrollment) to determine is a change in the assumption and sample size determination need adjustment.

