3.0 Patient Selection

3.1 Conditions for patient eligibility

- **3.1.1** All patients must be willing and capable of providing informed consent to participate in the protocol.
- 3.1.2 Patients must have appropriate staging studies identifying them as AJCC stage II or III non-small cell lung cancer, (according to AJCC Staging, 6th edition; see appendix III), or recurrent non-small cell lung cancer. Histologic confirmation of cancer will be required by biopsy or cytology within 9 months of study enrollment.
- **3.1.3** Patients must have the potential for benefit from local therapy (at the discretion of the investigator).
- **3.1.4** The patient's Zubrod performance status must be 2 or greater, OR patients with Zubrod performance status 0-1 and weight loss >10% over the last 6 months prior to enrollment,

OR patients determined to be medically unfit or refusing combined modality therapy are considered eligible.

- **3.1.5** Age ≥ 18.
- **3.1.6** Patients must have measurable or evaluable disease by RECIST 9.3 criteria.
- **3.1.7** Women of childbearing potential and male participants must agree to use an effective method of contraception.

Women of child-bearing potential and men must agree to use adequate contraception (hormonal or barrier method of birth control; abstinence) prior to study entry, for the duration of study participation, and for 90 days following completion of therapy. Should a woman become pregnant or suspect she is pregnant while participating in this study, she should inform her treating physician immediately.

A female of child-bearing potential is any woman (regardless of sexual orientation, having undergone a tubal ligation, or remaining celibate by choice) who meets the following criteria:

- * Has not undergone a hysterectomy or bilateral oophorectomy; or
- * Has not been naturally postmenopausal for at least 12 consecutive months (i.e., has had menses at any time in the preceding 12 consecutive months).
- **3.1.8** Patients must sign study specific informed consent prior to study enrollment.
- **3.1.9** While patients randomized to the standard arm (Arm B, 30-33 fractions) may receive concurrent chemotherapy with carboplatin/taxol at their treating physician's discretion, patients enrolled to the experimental arm (Arm A, 15 fractions) cannot be treated with concurrent chemoradiation and must not have plans for concurrent chemoradiation therapy. Sequential chemotherapy (prior to or after radiotherapy) is allowed for either arm.

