7.0 Drug Therapy

At the treating physician's discretion, chemotherapy may be administered concurrently ONLY to patients enrolled on the standard arm (30 fractions) using a combination of carboplatin and paclitaxel (Taxol) with standard dosing for concurrent chemo-radiotherapy in lung cancer. Patients treated on this arm, however, may not receive any other chemotherapy regimens, targeted therapy, or drugs known to act as radiosensitizers. Patients on the experimental arm (15 fractions) may NOT receive any concurrent chemotherapy, targeted therapy or drugs known to act as radiosensisitizers. Patients on either arm of the study may go on to receive adjuvant chemotherapy if determined appropriate by their medical oncologist one week after completing radiation therapy.

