11.1.2.4 Toxicity: Grade 3-5 adverse events as graded by CTCAE v 4.0

11.2 Sample Size Determination

The sample size calculation is based on the primary endpoint, overall survival at 1 year, and the assumption that patients are randomized until the end of accrual. The sample size is calculated with the 2-sided significance level of 0.05 and 80% statistical power using a 2-sample log rank test. We assume that the overall survival function follows an exponential distribution for each arm. Accrual to the study is assumed to be uniformly distributed. The null hypothesis is that the there are no difference in 1-year survival rates between two arms. We assume that the patients will be accrued for 2 years with a 1-year follow-up. We hypothesize that the patients randomly assigned to the control arm and experimental arm have a 1-year survival rate of 45% (hazard rate [λc]) of 0.799) and 60% (hazard rate [λe]) of 0.511), respectively, which is translated to the hazard ratio of $\lambda e/\lambda c = 0.640$. One interim analysis and a final analysis are planned for early stopping for efficacy. The efficacy testing is based on the Lan-DeMets spending function, which resembles the O'Brien-Fleming boundary. The total sample size of 226 patients (113 in the control arm and 113 in the experimental arm) will be accrued to achieve the desired 80% statistical power and 2-sided significance level of 0.05. Guarding against ineligibility or lack-ofdata rate of up to 5%, the final targeted accrual for this study will be 238 patients (119 per arm). Sample size was estimated using the sample size software EaST version 5.

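### The claim that control-arm-only concurrent chemotherapy leaves the power assumptions intact is unsupported, and intended use is not recorded before allocation

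*Combined protocol and SAP*

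**What the plan says.** Section 7.0 states that "chemotherapy may be administered concurrently ONLY to patients enrolled on the standard arm (30 fractions"), at the treating physician's discretion; sections 1.4 and 3.1.9 agree. Arm A may not receive it under any circumstances. Sequential chemotherapy is allowed in both arms.

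On the consequence for the design, section 1.4 says "Survival estimates related to the power and sample size determination of the study in all likelihood will not be affected", because concurrent therapy has not been shown superior to radiation alone in poor performing patients. It then promises a sensitivity analysis at the interim. Section 11.5.9 specifies this as a comparison of the first 44 patients, enrolled while concurrent chemotherapy was barred, with later patients.

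Eligibility (3.1.4) covers Zubrod 2 or greater, and Zubrod 0-1 with more than 10% weight loss. It adds: "OR patients determined to be medically unfit or refusing combined modality therapy are considered eligible". The background (1.1) says: "The best method found to date for improving the efficacy of radiation therapy for locally advanced NSCLC is to combine it with chemotherapy". It places the added benefit of concurrent over sequential treatment in good performance status patients.

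Section 11.2 sets the design: "The sample size is calculated with the 2-sided significance level of 0.05 and 80% statistical power using a 2-sample log rank test". Survival is taken to be exponential in both arms, and the timetable is that "patients will be accrued for 2 years with a 1-year follow-up". The 1-year survival rates are 45% and 60%. Objective 2.1 names only the two radiation approaches. Randomization (11.4) is stratified by Zubrod 2 versus above 2 and by stage.

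**The concern.** An active co-treatment has been added to one arm, while the 45% control rate has no allowance for it. That rate is close to the 44% that section 1.1 reports for a poor-risk trial of 60 Gy alone or with interferon. Section 1.4 itself says that concurrent chemotherapy in the experimental arm would disrupt the hypothesis test. The same reasoning applies when only the comparator receives it.

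Two things are at stake. First, if chemotherapy prolongs survival in some Arm B patients, the true difference is smaller than 45% versus 60% and power is below 80%. Second, a null result could mean that hypofractionation adds nothing, or that chemotherapy lifted the control arm. The toxicity, quality-of-life and cost comparisons carry the same mixture.

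The eligibility checklist, the registration procedures (5.2, 12.3) and the strata (11.4) contain no statement, made before allocation, of whether chemotherapy would be given. Arm B recipients therefore have no identifiable counterparts in Arm A, and an analysis by treatment received would be confounded by the physician's selection.

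**Working it through.** **1. The plan's own figure.** Inputs from 11.2: control hazard -ln(0.45) = 0.799; experimental hazard -ln(0.60) = 0.511; hazard ratio (HR) 0.640; two-sided 0.05; 80% power.

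- Events (Schoenfeld): 4 × (1.960 + 0.842)² / (ln 0.640)² = 158.
- Probability of death with uniform accrual over A years and F years of follow-up: 1 - [exp(-λF) - exp(-λ(A+F))]/(λA). With A = 2, F = 1: control 0.775, experimental 0.624, mean 0.700.
- 158 / 0.700 = 226.

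The stated 226 reproduces, with 80.2% power. There is no arithmetic error.

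**2. Power if control survival is higher.** N = 226, 2+1 years, experimental arm fixed at 60%. Power = Φ(√(d/4) × |ln HR| - 1.96), where d is the expected number of deaths.

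| Control 1-year survival | HR | Deaths | Power |
|---|---|---|---|
| 45% | 0.640 | 158 | 80% |
| 47.5% | 0.686 | 156 | 65% |
| 50% | 0.737 | 153 | 47% |

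**3. Translation into uptake and effect.** Neither is given in the documents; both are assumptions. With uptake f and chemotherapy hazard ratio h, control 1-year survival = (1-f) × 0.45 + f × 0.45^h, where 0.45^0.85 = 0.507 and 0.45^0.70 = 0.572. The value 0.70 is 9.6/13.7, the ratio of medians in the sequential-chemotherapy trial cited in 1.1. It serves only as an optimistic bound on the chemotherapy effect.

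Example: f = 20%, h = 0.85 gives 0.8 × 0.45 + 0.2 × 0.507 = 46.1%, HR 0.661, power 74%.

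To exclude the first 44 patients from uptake, assume that they split 22 per arm. Effective uptake is then f × 91/113 = 0.805f. The last column also uses the 60-month accrual of 11.3 with 1 year of follow-up, where power without chemotherapy is 87%.

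| h | f | 2+1 years | 2+1, first 44 excluded | 5+1, first 44 excluded |
|---|---|---|---|---|
| 0.85 | 20% | 74% | 75% | 82% |
| 0.85 | 50% | 63% | 66% | 74% |
| 0.70 | 20% | 66% | 69% | 77% |
| 0.70 | 50% | 39% | 48% | 56% |

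These figures treat the mixed control arm as exponential. A log-rank calculation on the mixture itself is up to about 2 points lower in the 2+1 column.

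**4. What can still be compared without chemotherapy.** The first 44 patients were randomized with concurrent chemotherapy barred in both arms. Under the plan's assumptions they yield 44 × 0.700 = 31 deaths and about 24% power at HR 0.640.

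If intent had been recorded for all 226 patients and 20%, 30% or 50% had declared 'yes', the 'no' group would have about 127, 111 or 79 deaths. Its power at HR 0.640 would be 71%, 65% or 51%.

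**The case against.** The statement is hedged, and a safeguard follows it at once. Section 1.4 observes that the trials showing benefit often left out patients with marked weight loss, so the Zubrod 0-1 weight-loss route is not ignored. Section 1.1 confines the concurrent benefit to good performance status patients. Those eligible because they refuse or cannot tolerate combined therapy are the least likely to receive it, and 7.0 only permits chemotherapy. All of this stands. A reader might infer that eligibility and background contradict the power claim. They do not; they leave it without support.

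A reader might also take 39% as the expected power. It rests on a hazard ratio from a sequential trial, and sequential chemotherapy is open to both arms here. It also ignores the first 44 patients and the longer accrual. Nor is it right that no clean comparison exists, since the first 44 provide one, though a small one.

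The interim safeguard does not remove the concern. Early versus later patients is a non-randomized comparison, confounded with calendar time. There is no rule for changing the sample size. The timing differs between 1.4 (50% enrollment) and 11.5.9 (half of patients followed for 1 year). It also cannot separate fractionation from chemotherapy.

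**Conclusion.** The concern holds as a cheap improvement. The sponsor may choose a comparator that permits chemotherapy, and the intent-to-treat comparison remains valid for that question. What does not follow is that the survival assumptions are unaffected: 80% power requires that chemotherapy be unused or have no effect, and the documents establish neither.

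At 20-50% uptake and HR 0.85, power is about 74-63% on the plan's 2+1-year basis. Allowing for the first 44 patients and 60-month accrual, it is about 82-74%. The HR 0.70 range (66-39% and 77-56% respectively) is a bound, not an expectation. All of these figures rest on assumed uptake and effect, exponential survival and N = 226.

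The lasting loss is interpretive. Intent that is not recorded before allocation cannot be validly reconstructed afterwards.

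**What to change.** 1. For all future patients, add a registration field, completed before allocation: would concurrent carboplatin/paclitaxel be intended if the patient were assigned to Arm B (yes/no)? Pre-specify a supportive analysis stratified by this field, with the effect in the 'no' group as the fractionation comparison. Patients enrolled after the amendment but without the field form a 'not recorded' group, kept apart from the first 44.
2. Restate objective 2.1 as hypofractionated radiotherapy without concurrent chemotherapy versus standard radiotherapy with or without it.
3. Replace the reassurance in 1.4 with power at control 1-year survival of 45%, 47.5% and 50%: 80%, 65% and 47% under the 2+1-year design.
4. Reconcile section 1.2, which still says that this protocol excludes concurrent chemotherapy, with 1.4, 3.1.9 and 7.0. Reconcile 3.1.4 with 7.0 for patients enrolled as unfit for or refusing combined therapy.

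The cost is one field, some wording and a less favorable stated power; care does not change. The main drawback is that the 'no' group is underpowered: 71%, 65% or 51% if 20%, 30% or 50% declare 'yes', and lower in practice because the field starts mid-trial.
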